## INTRODUCTION

Myopia known as “short sightedness” causes blurring of vision for distant objects but clearer for near objects. In myopic eyes, the light comes to a focus point before it reaches the retina. When moving closer to an object, this changes the focusing of the light and the object is then in focus on the retina and so looks clearer. Myopia depends on the length of the globe, the corneal steepness, and the lens power.

Classification of myopia:

- Mild myopia: power up to - 4.00 diopters (D)
- Moderate myopia: -4.00D to -8.00D
- High myopia: > -8.00D

ICL implantation can correct myopia, hyperopia, or astigmatism, with clinical and visual results as good as or better than laser procedures. Patients who are not suitable candidates for corneal reshaping procedures, and in whom optical correction with spectacles or contact lenses is either challenging or have poor results, can benefit from ICL surgery.

One of the problems for LASIK application for myopic patients is the risk of post-LASIK ectasia which is believed to be reduced using femto LASIK and the ability of creation of smaller flap thickness. Less high order aberrations are induced with femto LASIK compared to the conventional approach. Results in terms of contrast sensitivity, especially in high spatial frequencies, are better with femto LASIK compared to the conventional method.

This study evaluates the effect of each modality treatment on the visual outcomes in treatment moderate myopic patients.

Phakic intraocular lenses (PIOLs) are generally accepted as an alternative treatment for ametropic correction among different types of refractive correction. Rapid visual recovery, high efficacy, predictability and stability of visual quality, preservation of accommodation, and reversibility are several privileges that have been attributed to PIOL implantation.

The Visian Implantable Collamer Lens (ICL; STAAR Surgical Co, Monrovia, California) is approved by the United States Food and Drug Administration (FDA) for the treatment of moderate to severe myopia. The lens material, trade-named Collamer, is a hydrophilic collagen-polymer combination with a water content of 34% and a refractive index of 1.45.

Recently, a new ICL (V4c) , with a 360  $\mu\text{m}$  central hole that allows for the natural flow of aqueous humor without the need for a peripheral iridotomy, which may reduce the risk of anterior capsular opacification and cataract formation comparing to the old forms of ICL. Previous studies have shown that the pupil constriction in response to light can affect the vault, eventually causing the ICL to move posteriorly towards the crystalline lens, leading to a significant decrease in central vault under photopic conditions.

Femtosecond (FS) laser is an infrared laser with a wavelength of 1053 nm. It works by producing photo-disruption or photoionization of the optically transparent tissue such as the cornea. Application of FS results in the generation of a rapidly expanding cloud of free electrons and ionized molecules. The acoustic shock wave generated results in disruption of the treated tissue.

FS laser has pulse duration ranging 10 to 15 seconds. Reducing the pulse duration reduces the amount of collateral tissue damage which makes FS laser safe to be used in corneal surgeries.

The Wave Scan Wave Print System (Visx, Inc.) is a diagnostic instrument designed to measure and display refractive errors and wave front aberrations of the eye using a Hartmann-Shack wave front sensor. A small spot of laser light is projected onto the retina and reflects back through the pupil. The light exiting from the eye is imaged by a lens let array, and the array of spot images is captured by a video sensor. The location of each spot gathered from the video sensor is then compared to the theoretical ideal locations, and the eye's wave front aberrations are computed. The measurements with this device are centered on the center of the entrance pupil and taken without pupil dilation.

Contrast sensitivity is defined as the inverse of the contrast value at threshold. Contrast sensitivity is plotted on a chart in which the x axis is the spatial frequency, and the y axis is contrast sensitivity in log scale. Spatial frequency is specified in cycles per degree (cpd), which corresponds to the spatial frequency of the sine wave grating in terms of size, using cycles per degree of visual angle as the unit. Maximal contrast sensitivity function is at 3 to 6 cpd. The curve of contrast sensitivity is bell shaped. At the high frequency end, where contrast sensitivity is lowest, 100% contrast is needed, it corresponds to visual acuity. 

## **AIM OF THE WORK**

This study aims to compare visual outcomes after Femto LASIK and implantable collamer lens in treatment of moderate myopia.

## SUBJECTS & METHODS

- **Type of Study:** Prospective observational study
- **Study Setting:** Magrabi Eye Hospital, Cairo, Egypt
- **Study Period:** 24 months. The patient will be assessed on interval: preoperatively, 1 month, 3 months and 6 months postoperatively.
- **Study Population:**
  - *Inclusion Criteria:*
    - Moderate myopia (-4D to -8D)
    - Age >18 years
    - Clear optical media
    - No ocular pathology
  - *Exclusion Criteria:*
    - Mild (<-4D) or high (>-8D) myopia, hyperopia
    - Patients with media opacity
    - Patients with associated ocular pathology
    - Patients with corneal topography not fitting to either treatment modalities
- **Sampling Method:** Convenience non-random sampling technique will be followed

- **Sample Size:** 120 eyes will be included in the study, and they will be divided into four groups:
  - Group 1: includes 60 eyes undergoing ICL surgery
    - Divided into two subgroups:
      - Group 1A: includes patients with simple myopia
      - Group 1B: includes patients with compound myopic astigmatism
    - Group 2: includes 60 eyes undergoing femtoLASIK surgery
      - Divided into two subgroups:
        - Group 2A: includes patients with simple myopia
        - Group 2B: includes patients with compound myopic astigmatism
- **Ethical Considerations:** This study will be conducted after the approval of the institutional ethical committee and after obtaining an informed written consent from every patient
- **Study Tools:**
  - Slit Lamp Biomicroscopy
  - Pentacam for full corneal topography profile (Oculus)
  - Wave scan J&J vision Visx for assessment of aberrations
  - PeliRobson Chart for testing of contrast sensitivity
- **Study Procedure:** Patients will be diagnosed according to:
  - Full detailed history
  - Complete clinical ophthalmological examination including visual acuity assessment with best correction, anterior segment examination, IOP measurement, fundus examination, cycloplegic refraction and contrast sensitivity testing
  - Investigations: corneal topography, aberrations screening
  - Post-operative follow up including visual acuity assessment with best correction, aberrations screening and contrast sensitivity testing on interval 1 month, 3 months and 6 months postoperatively

**Statistical Analysis & Package:** The collected data will be revised, coded, tabulated, and introduced to a PC using statistical package for social sciences (IBM SPSS 20.0). Data will be presented and suitable analysis will be done according to the type of data obtained for each parameter.

- *Descriptive Statistics:*

- Mean, Standard deviation ( $\pm SD$ ) and range for parametric numerical data, while Median and Interquartile range (IQR) for non-parametric data

- Frequency and percentage of non-numerical data

- *Analytical Statistics:*

- Pearson Correlation Coefficient (r): Correlation was used as a measure of the strength of a linear association between two quantitative variables. The Pearson correlation coefficient, r, can take a range of values from +1 to -1. A value of 0 indicates that there is no association between the two variables. A value greater than 0 indicates a positive association; that is, as the value of one variable increases, so does the value of the other variable. A value less than 0 indicates a negative association; that is, as the value of one variable increases, the value of the other variable decreases

- P-value: Level of significance:

- P>0.05: Non significant (NS)
- P<0.05: Significant (S)
- P<0.01: Highly significant (HS)

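### The ICL versus femto-LASIK comparison is non-random over a -4 D to -8 D range and no adjustment for preoperative refraction is specified, so an imbalance in dioptres can bias it

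*Combined protocol and SAP*

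**What the plan says.** All of the following comes from SUBJECTS & METHODS in the combined protocol and SAP.

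- **Range.** Inclusion requires "Moderate myopia (-4D to -8D". The exclusions repeat the same limits: "Mild (<-4D) or high (>-8D) myopia, hyperopia". The plan does not say whether these limits mean sphere or spherical equivalent.
- **Design and sampling.** The study is a "Prospective observational study", and "Convenience non-random sampling technique will be followed".
- **Groups.** "120 eyes will be included in the study, and they will be divided into four groups". "Group 1: includes 60 eyes undergoing ICL surgery", and Group 2 has 60 femto-LASIK eyes. The only further split is simple myopia against compound myopic astigmatism. That separates eyes by cylinder, not by amount of myopia, and no subgroup sizes are given.
- **Baseline measurement.** The work-up includes "fundus examination, cycloplegic refraction and contrast sensitivity testing". The refraction is therefore available, but it has no stated role in the analysis.
- **Analysis.** Statistical Analysis & Package lists descriptive statistics, the Pearson correlation and P-value labels, with a general promise that the analysis will suit the type of data. It names no between-group test, covariate, regression or matching.

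**The concern.** The refractive error is the amount of correction each procedure has to deliver. It can vary twofold within the eligible range. Neither enrolment nor analysis keeps the two groups comparable on it.

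If outcome depends on the dioptres corrected, after one procedure or both, a difference in mean refraction between groups will appear as a difference between procedures. AIM OF THE WORK contains only that comparison. A significant result could then not be attributed to the procedure, and a real difference could be masked.

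This is one specific, measured confounder with a specific remedy. Enrolling eligible patients consecutively, or clarifying the topography exclusion, would not by itself remove it, because the choice of procedure could still follow refraction among eyes suited to both.

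**Working it through.** **The plan's own figures.** The range ratio is 8/4 = 2.0. The total is 60 + 60 = 120 eyes. That number cannot be re-derived, because no effect size, SD or power is given. For scale, with 60 per group and two-sided 5% (sidedness is not stated), the detectable difference at 80% power is (1.96 + 0.84) × √(2/60) = 0.51 SD.

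**Assumptions not in the documents.** No true procedure effect; 60 independent eyes per group; refraction SD 1 D within each group, on 4-8 D and centred on 6 D overall; outcome SD 1; correlation r between dioptres and outcome of 0.2 to 0.4; a gap g in mean dioptres between groups.

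**Case A: the same slope after both procedures.** Spurious difference b = r × g / 1 D. SE = √(2/60) = 0.183. False-positive rate = Φ(b/SE − 1.96) + Φ(−b/SE − 1.96).

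- g = 1 D, r = 0.2: b = 0.20, b/SE = 1.10, rate 19.5%.
- g = 1 D, r = 0.4: b = 0.40, b/SE = 2.19, rate 59%.

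**Case B: a slope after LASIK only, procedures equal at 6 D.** Only the LASIK mean is displaced, by g/2 from 6 D, so b = r × g/2. SE = √((1 + 1 − r²)/60).

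- g = 1 D, r = 0.2: b = 0.10, SE = 0.181, b/SE = 0.55, rate 9%.
- g = 1 D, r = 0.4: b = 0.20, SE = 0.175, b/SE = 1.14, rate 21%.

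Simulation with dioptres confined to 4-8 D agrees with these formulas to within about two percentage points:

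| Gap in mean dioptres | Case B, unadjusted (r = 0.2-0.4) | Case A, unadjusted (r = 0.2-0.4) |
|---|---|---|
| 0.5 D | about 6-9% | about 8-18% |
| 1.0 D | about 10-21% | about 19-60% |
| 1.5 D | about 14-42% | about 36-90% |

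With preoperative dioptres as a covariate, the rejection rate returns to about 5%. With no gap, both analyses stay at about 5%.

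**If patients contribute both eyes.** The plan counts eyes and does not say how many patients supply them. Suppose every patient supplies two, with a residual within-patient correlation of 0.6 (assumed). The variance of a group mean is inflated by 1 + 0.6 = 1.6. A covariate model that treats eyes as independent then rejects with probability 2 × [1 − Φ(1.96/√1.6)] = 2 × [1 − Φ(1.55)] = 12%. The covariate alone is not enough in that case.

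**The case against.** The strongest reply is that imbalance is possible but not shown. With SD 1 D and 60 independent eyes per group, chance alone gives a difference in means with SE √(2/60) = 0.18 D. A gap of 1.0 to 1.5 D would need strong channelling of patients by refraction, and the documents do not demonstrate it. This stands, and it is why the size of the bias is stated only as a range under assumptions.

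A reader might infer from the Introduction, which offers ICL to "Patients who are not suitable candidates for corneal reshaping procedures", that ICL eyes will lie nearer -8 D and LASIK eyes nearer -4 D. That sentence is general background. It makes non-random choice plausible, but says nothing about where eyes fall within the eligible range. If every enrolled eye suited both procedures, it would not apply at all.

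A reader might also add spectacle minification as a mechanism for acuity. At an assumed 12 mm vertex distance, a 1 D gap (6.5 against 5.5 D) is worth log10(1.078/1.066) = 0.005 logMAR. It also enters only through the preoperative spectacle measurement, so it matters only if change from baseline is analysed. The point does not rest on it. Nor do the documents establish that every outcome depends on dioptres.

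Finally, the general promise of an analysis fitted to the data does not rule out adjustment. But it does not specify one, and the only named analytical statistic, the Pearson correlation, adjusts for nothing.

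**Conclusion.** The omission is certain: the comparison is non-random across 4 D of eligible myopia, and no part of the plan balances or adjusts preoperative refraction. The resulting bias is possible and its size is unknown. Under the stated assumptions, a 1 D gap raises a nominal 5% error to about 10-21% if outcome depends on dioptres only after LASIK, and to about 19-60% if it does so equally after both procedures. The lower range fits better the argument that more dioptres mean more corneal reshaping, since that applies only to LASIK.

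The documents do not support saying that the groups will differ, in which direction, or that the result will be wrong. Adjustment for refraction removes this one source of bias if its form is right. It does not remove other confounding from non-random allocation.

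**What to change.** In Statistical Analysis & Package, prespecify that:

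1. every ICL versus femto-LASIK comparison is adjusted for preoperative spherical equivalent, as a continuous variable from the cycloplegic refraction already taken, and for the baseline value of the outcome;
2. a procedure-by-refraction term is examined, because the slope may differ by procedure, with refraction centred at a stated value so that the procedure difference has a clear meaning;
3. preoperative refraction is tabulated by procedure group;
4. if patients contribute both eyes, the model accounts for within-patient correlation, for example by a mixed model or generalised estimating equations.

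The cost is analysis wording and model fitting. No new measurement or extra eyes are needed, and the total stays at 120. Recruiting equal numbers within refraction bands is optional. It would secure overlap between groups but may slow recruitment, and it is not part of the required change.

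### Convenience sampling leaves entry to each surgical group to unrecorded discretion; consecutive enrolment within each procedure, with a screening log, would reduce and document this at small cost

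*Combined protocol and SAP*

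**What the plan says.** Under SUBJECTS & METHODS the design is a "Prospective observational study" at one hospital, with a 24-month study period and visits at 1, 3 and 6 months after surgery. The sampling rule is one line: "Convenience non-random sampling technique will be followed". On size, "120 eyes will be included in the study"; one group "includes 60 eyes undergoing ICL surgery" and the other "includes 60 eyes undergoing femtoLASIK surgery". AIM OF THE WORK is comparative: "This study aims to compare visual outcomes after Femto LASIK and implantable collamer lens in treatment of moderate myopia".

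The protocol has no consecutive-enrolment rule and no screening or refusal log. It does not say who selects patients, or how a patient comes to have one operation rather than the other. The Statistical Analysis & Package section names Pearson correlation as its only analytical method. It plans no baseline comparison, no adjustment and no method for missing data.

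**The concern.** Two steps decide which eyes are compared. First, patient and surgeon settle on ICL or femto LASIK. Second, among eligible patients having a given operation, some are entered in the study and some are not. The sampling sentence governs only the second step, and it leaves that step open.

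The two groups are filled separately, each to 60 eyes. If entry in one group leans more than in the other towards patients with better prospects, the difference between group means moves even when the operations perform equally. If entry leans the same way in both, the contrast is largely untouched, and the main loss is in how far the results apply to other patients. With no list of eligible patients left out, neither the authors nor a reader could tell these situations apart, and such a list is hard to rebuild afterwards.

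**Working it through.** **Inputs from the protocol.** 60 eyes per group and a 5% significance level. The protocol gives no power, effect size, SD or between-group test, so the 120 eyes cannot be reproduced.

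**Assumptions.** Two-sided t test; eyes treated as independent (the number of patients is not stated); a selection factor whose correlation ρ with the outcome is 0.2 to 0.5; and the enrolled fractions shown below. None of these comes from the documents.

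**Step 1: what 60 per group can detect.** With the normal approximation at 80% power, (1.960 + 0.842) × √(2/60) = 0.51 SD. The exact t calculation gives 0.52 SD.

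**Step 2: shift from selection.** If the more favourable fraction f of eligible patients is enrolled, the group mean moves by ρ × λ(f) SD. Here λ(f) = φ(z)/f, φ is the standard normal density, and z is the cut-off leaving f above it.

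- λ(0.5) = 0.399/0.5 = 0.798
- λ(0.6) = 0.386/0.6 = 0.644
- λ(0.8) = 0.280/0.8 = 0.350
- λ(0.9) = 0.175/0.9 = 0.195
- λ(1) = 0

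The bias in the comparison is ρ × [λ(f₁) − λ(f₂)]. The rejection rate is that of the 5% test when there is no true difference, from the noncentral t distribution with 60 per group.

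| Fraction enrolled, one group v the other | Bias, ρ = 0.2 to 0.5 | Rejection rate |
|---|---|---|
| Equal | 0 | 5% |
| 50% v 60% | 0.03 to 0.08 SD | 5.3% to 7.0% |
| 80% v 90% | 0.03 to 0.08 SD | 5.3% to 7.0% |
| 80% v all | 0.07 to 0.18 SD | 7% to 16% |
| 50% v 80% | 0.09 to 0.22 SD | 8% to 23% |
| 50% v all | 0.16 to 0.40 SD | 14% to 58% |

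For example, 50% v all at ρ = 0.5 gives 0.5 × 0.798 = 0.40 SD, and 50% v 60% at ρ = 0.5 gives 0.5 × (0.798 − 0.644) = 0.08 SD. All rows assume selection in the same direction in both groups, or in one group only. Selection in opposite directions would add rather than cancel.

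**Step 3: what consecutive enrolment leaves behind.** A simulation of 2,000,000 subjects with no treatment effect and ρ = 0.5 let prognosis influence both choice of surgery and entry. Each influence was a log-odds slope per SD of prognosis. Choice slopes were 0, 0.5 and 1. Entry slopes were 0 (consecutive enrolment), 0.5 and 1.

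| Choice-of-surgery slope | Bias, entry slopes opposite in the groups (0.5; 1) | Bias, entry slopes the same (0.5; 1) | Bias, consecutive entry |
|---|---|---|---|
| 0 | 0.24; 0.41 SD | 0; 0 | 0 |
| 0.5 | 0.44; 0.59 SD | 0.22; 0.20 SD | about 0.24 SD |
| 1 | 0.59; 0.70 SD | 0.39; 0.35 SD | about 0.41 SD |

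Consecutive entry removes the part due to differential entry. The part due to choice of surgery stays; by the normal approximation, 0.24 and 0.41 SD correspond to false-positive rates of about 25% and 62%. Where entry leans the same way in both groups, consecutive entry does not improve the contrast: its bias is slightly larger than before (0.24 against 0.20 to 0.22 SD in the middle row).

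**The case against.** The strongest reply is that the bias is conditional. Both groups come from one hospital under one eligibility list, and the sampling label could mean no more than taking whoever is available. If entry leans similarly in the two groups, the shift is at most a few hundredths of an SD. The larger figures need strong favourable selection in one group and none in the other, or selection in opposite directions. This stands, and it is why the range must be shown from zero.

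A reader might infer that staff pick patients by expected result or likelihood of return. The protocol does not name a selector or a criterion. What it shows is that entry is left open and nothing is recorded.

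A reader might also infer that consecutive enrolment would largely repair the comparison. It would not. Choice of surgery is a separate source of confounding, untouched by the sampling rule. If present entry favours patients likely to attend, inviting everyone may turn selection at entry into missed visits at 1, 3 and 6 months, for which no missing-data method is named.

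Finally, the cost cannot be verified: no case volume or staffing is given. That argues for stating the downsides, not for keeping the present rule. The remedy adds no procedure, leaves the enrolment target unchanged and respects the observational design. Leaving the simple-myopia and astigmatism subgroup sizes to chance is no new loss, since the protocol sets no size for them.

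**Conclusion.** The point holds as a worthwhile, inexpensive improvement. The plan commits to a sampling rule that leaves entry to unrecorded discretion in a study whose sole aim is a between-group comparison, and nothing elsewhere in the plan offsets it.

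The size is unknown. Under the assumptions above the shift runs from 0, through 0.03 to 0.08 SD for similar but unequal selection, to 0.16 to 0.40 SD when the better half is enrolled in one group only. The top of that range approaches the 0.52 SD that the study could detect. The rejection rates also assume independent eyes, so they would change if both eyes of a patient are used.

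The documents do not support saying that the comparison is biased, that staff choose the patients, or that this change alone would make the comparison sound. They support saying that the plan could neither prevent nor detect differential entry.

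**What to change.** Replace the sampling sentence with:

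> Within each procedure, all consecutive eligible patients having ICL or femto LASIK at the hospital from the start date are invited until 60 eyes per group are enrolled. A screening log, as the ethics committee permits, records eligible patients not enrolled (age, sphere, cylinder, procedure, reason), and enrolled and non-enrolled patients are compared by group.

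Add that this reduces and documents selection at entry but does not address confounding by choice of surgery or loss to follow-up, which need their own provisions.

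The log depends on a clear definition of an eligible patient. One exclusion, "Patients with corneal topography not fitting to either treatment modalities", can be read as unsuitable for both operations or for any one of them, so the authors should state which is meant.

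**Cost.** Some clerical work, possible ethics agreement to hold data on people not enrolled, and groups that may fill at different times. If all six-month visits must fall within the 24 months, 24 − 6 = 18 months remain for enrolment, or 60/18 = 3.3 eyes per month per group; the authors should check this against their case volume. Missed visits would leave fewer than 60 eyes per group for analysis unless more are enrolled.

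### The sample is counted as 120 eyes with no patient count, eye-selection rule or method for fellow-eye correlation; if same-group pairs are analysed by eye, p-values will be too small

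*Combined protocol and SAP*

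**What the plan says.** Under Subjects & Methods, the Sample Size item counts eyes: "120 eyes will be included in the study, and they will be divided into four groups". The ICL arm reads "Group 1: includes 60 eyes undergoing ICL surgery", and the femtoLASIK arm also has 60 eyes.

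Elsewhere in the same section the unit is the patient:

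- Subgroups: "Group 1A: includes patients with simple myopia", with the other three subgroups worded the same way.
- Consent: "obtaining an informed written consent from every patient".
- Follow-up: "The patient will be assessed on interval: preoperatively, 1 month, 3 months and 6 months postoperatively".
- Most exclusion criteria are also worded per patient.

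Statistical Analysis & Package commits to little: "Data will be presented and suitable analysis will be done according to the type of data obtained for each parameter". The one inferential method it names is correlation: "Pearson Correlation Coefficient (r): Correlation was used as a measure of the strength of a linear association between two quantitative variables". Results are then labelled significant below 0.05 and, at the stricter level, "P<0.01: Highly significant (HS").

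The text gives no number of patients, no rule on one or both eyes, no way to choose a study eye, and no rule on whether a patient's two eyes must have the same procedure. It names no between-group test and no method for clustered eyes.

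**The concern.** Two eyes of one person share genetics, age, refractive history and often the surgical session, so their outcomes are usually positively correlated. A t-test, rank test or Pearson coefficient run over eyes treats them as unrelated. If fellow eyes sit in the same group, the standard error of the group difference is then too small and so are the p-values.

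Comparing the two procedures is the study's only stated aim, and the plan attaches verbal labels to p-values at 0.05 and 0.01. Under that condition both labels would be awarded more often than their nominal rates when there is no difference, and 60 eyes per group would overstate the information collected.

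The direction depends on the missing rule. If each patient had one eye in each group, an unpaired test would err the other way and lose power. A reader of the plan cannot tell which case applies.

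A related gap is that subgroups A and B are defined by patient. A patient with one simple-myopia eye and one astigmatic eye has no defined subgroup.

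**Working it through.** **From the documents.** 60 eyes per group and significance levels 0.05 and 0.01. Two-sided testing is assumed, since sidedness is not stated.

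**Assumed, because the documents give no value.** Inter-eye correlation ρ from 0.3 to 0.9; share f of eyes that belong to same-group pairs; a between-group test that treats eyes as independent.

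**The plan's own figure.** The 120 eyes cannot be reproduced, because no effect size, SD, power or dropout is given. Working backwards with independent eyes, the difference detectable with 80% power is (1.960 + 0.842) × √(2/60) = 0.51 SD.

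**Number of patients.** 120 eyes can come from 120 / 2 = 60 patients up to 120 patients.

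**Fellow eyes in the same group.**

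- Variance inflation = 1 + fρ
- True error = 2 × [1 − Φ(z / √(1 + fρ))], with z = 1.960 or 2.576
- Effective eyes per group = 60 / (1 + fρ)
- Detectable difference = 2.802 × √(2 / effective eyes)

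Example with f = 1, ρ = 0.5: 1.960 / √1.5 = 1.600, so the true error is 10.95%. Effective eyes are 60 / 1.5 = 40.

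| Case | ρ | True error at 5% | True error at 1% | Effective eyes per group | Detectable difference (SD) |
|---|---|---|---|---|---|
| All eyes paired (30 patients per group) | 0.3 | 8.6% | 2.4% | 46.2 | 0.58 |
| | 0.5 | 10.9% | 3.5% | 40.0 | 0.63 |
| | 0.7 | 13.3% | 4.8% | 35.3 | 0.67 |
| | 0.9 | 15.5% | 6.2% | 31.6 | 0.71 |
| Half the eyes paired (45 patients per group) | 0.3 | 6.8% | 1.6% | 52.2 | 0.55 |
| | 0.5 | 8.0% | 2.1% | 48.0 | 0.57 |
| | 0.7 | 9.2% | 2.7% | 44.4 | 0.59 |
| | 0.9 | 10.4% | 3.2% | 41.4 | 0.62 |
| One eye per patient (60 patients per group) | any | 5.0% | 1.0% | 60 | 0.51 |

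Simulated t-tests by eye agree with the formula at the 5% level: about 8.5% to 15.9% with all eyes paired and 6.8% to 10.6% with half paired. A t-test on patient means, in simulation of the fully paired case, holds 5%.

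**One eye in each group (60 patients in total), unpaired test.** The variance factor is 1 − ρ. True error at nominal 5% is 1.9% at ρ = 0.3, 0.6% at ρ = 0.5, and below 0.1% at ρ = 0.7 or more.

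**Pearson r over 120 eyes, no true association.** If both variables have inter-eye correlation ρ, the variance of r is inflated by about 1 + fρ². With all eyes paired and ρ = 0.9 the factor is 1.81, giving 14.5% by formula and 14.8% in simulation; at ρ = 0.3 the error is about 6.0%. With half paired the range is about 5.5% to 9.8%.

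**The case against.** The strongest reply is that no error has been shown. The plan does not say that both eyes will enter or that the eye is the unit of analysis, and a promise of suitable analysis could include a clustered method. This stands in part: the inflation is conditional, and no figure above should be quoted as this trial's error rate. The 15.5% end needs every patient to be bilateral, every pair to lie in one group, and a correlation of 0.9. But the plan ties suitability to the type of data, which does not address dependence between eyes. An analyst who follows it over 120 eyes has no instruction to allow for pairing.

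Three further points have weight:

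- **Pearson.** The plan does not say which variables will be correlated. If either is weakly correlated between eyes, the inflation is smaller, and at ρ = 0.3 it is negligible.
- **GEE.** Without a small-sample correction it does not fully restore the error rate. With 30 patients per group, an uncorrected robust z-test on patient means rejects about 6% at nominal 5%.
- **Priority.** The plan also lacks a primary endpoint, a named between-group test and a sample-size basis, and its sampling is non-random. Fellow-eye handling is one part of a wider gap. That limits its rank among the problems but does not remove it.

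**Conclusion.** The concern holds as a conditional one and should be fixed. The omissions themselves are certain: the Subjects & Methods text contains no patient count, eye rule or fellow-eye method, and nothing elsewhere in the available text supplies them.

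The size of the effect is a range under stated assumptions. With same-group pairs analysed by eye and ρ of 0.3 to 0.9, the 0.05 label would be applied at a true rate between 6.8% (half the eyes paired, ρ = 0.3) and 15.5% (all paired, ρ = 0.9). The 0.01 label would be applied at between 1.6% and 6.2%. With one eye per patient there is no inflation. With fellow eyes split between the procedures, an unpaired test is conservative.

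**What to change.** 1. State the number of patients and of eyes per group, whether both eyes may enter, and whether one patient may contribute an eye to each group.
2. Define subgroups A and B by eye.
3. For between-group comparisons at a single visit, use a linear mixed model with a fixed effect for procedure and a random intercept for patient. If the 1-, 3- and 6-month visits are modelled together, add eye within patient. The patient intercept also covers a patient with one eye in each group.
4. GEE clustered on patient is an alternative and also suits non-normal or categorical outcomes. Specify a small-sample correction or a t reference. If every pair is in one group, a t-test on patient means is a simple valid option.
5. For correlations, use patient means or a patient-clustered regression.

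**Cost.** The change needs wording and a patient identifier on each eye's record; the mixed model or GEE needs no extra patients or visits. When eyes are paired, p-values will be larger and the stated precision lower. Pre-specifying one study eye per patient is also valid, but it could leave as few as 30 eyes per group. The detectable difference would then be 2.802 × √(2/30) = 0.72 SD, against 0.58 to 0.71 SD with both eyes modelled, unless more patients are recruited.
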